5.2 Pre-Treatment Criteria

5.2.1 Screening visit

All participants must sign an informed consent document prior to the initiation of any study related procedures. The informed consent document must be signed within 30 days of Cycle 1 Day 1. The remaining screening procedures (with the exception of the scans

and pre-treatment biopsy) are to be conducted within 21 days of Cycle 1 Day 1.

- Review of study eligibility criteria
- Physical Examination, including height and weight
- Medical History
- Record concomitant medications taken up to 14 days prior to Cycle 1 Day 1
- Vitals [temperature, heart rate (HR), blood pressure (BP) and respiratory rate (RR)]
- ECOG Performance Status evaluation
- Laboratory Assessments
 - Hematology: hemoglobin, hematocrit, red blood cell count, white blood cell count with differential and platelet count
 - Serum chemistry: sodium, potassium, chloride, bicarbonate, magnesium, calcium, phosphorus, blood urea nitrogen, creatinine, glucose (random), total bilirubin, LDH, total protein, ALP, ALT, AST, creatine phosphokinase, and albumin
 - Serum lipase and amylase
 - Serum pregnancy test for women of childbearing potential (WOCBP)
 - Prothrombin time (PT) and activated partial thromboplastin time (aPTT)
 - Urinalysis
- Echocardiogram (ECHO)
 - Unscheduled ECHOs can be completed as clinically indicated.
- 12-lead ECG. If an ECG shows QTc prolongation (>470 milliseconds), the ECG must be repeated twice to obtain values in triplicate.
- Ophthalmology examination: an ophthalmologist, or designated member of the clinical team, will check the participants vision and measure the pressure level in their eyes at baseline.
- Radiologic imaging studies to evaluate tumor status must include: Magnetic Resonance Imaging (MRI) of the brain and contrast Computed Tomography (CT) of the chest, abdomen, and pelvis. MRI of the chest, abdomen and/or pelvis may be used in place of a CT scan at baseline, but the same type of imaging modality must then be used throughout the course of the study (e.g. MRI of the pelvis performed at baseline, therefore, MRI of pelvis must be done at subsequent visits). Additional imaging may be obtained as clinically indicated. Baseline scans must be done ≤ 4 weeks prior to the start of study treatment.

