- Tumor biopsy 1 – 28 days prior to receiving the first dose of study treatment. Archival tissue from a biopsy taken within 6 months prior to the first study treatment may be used in place of a pre-treatment biopsy at the discretion of the PI.

5.2.2 Cycle 1, Day 1

- Physical exam
- Vital signs (temperature, HR, BP and RR)
- Weight
- Performance status
- Record concomitant medications
- Laboratory Assessments*
 - Hematology
 - Serum chemistry
 - Serum lipase and amylase
 - Serum pregnancy test for WOCBP
- 12-lead ECG. If an ECG shows QTc prolongation (>470 milliseconds), the ECG must be repeated twice to obtain values in triplicate.
- BVD-523 dosing
- Dispensing of study medication for the remainder of the 28 day cycle with drug diary.
- Record AEs

***NOTE:** C1D1 laboratory assessments are not required to re-meet eligibility criteria. If there is a cause for concern related to eligibility or scheduled C1D1 laboratory assessments the investigator should use their discretion.

5.2.3 Cycle 1, Day 15

- Tumor biopsy between days 12-18 while on treatment.
- Collection of research blood sample for PK analysis prior to dosing.

5.2.4 Cycle 2, Day 1

- Physical exam
- Vitals (temperature, HR, BP and RR)
- Weight
- Performance status
- Record concomitant medications
- Laboratory Assessments
 - Hematology

- Serum chemistry
- Serum lipase and amylase
- PT and aPTT
- Urinalysis
- Serum pregnancy test for WOCBP
- 12-lead ECG. If an ECG shows QTc prolongation (>470 milliseconds), the ECG must be repeated twice to obtain values in triplicate.
- BVD-523 dosing
- Dispensing of medication for the remainder of the 28 day cycle with drug diary.
- Record AEs
- Eye examination

5.2.5 Cycle 2, Days 22 – 28

- Radiologic imaging studies: CT or MRI of chest, abdomen and pelvis followed by response evaluation to evaluate tumor status are required at each tumor assessment visit, even if sites of disease were not identified in this region at baseline. MRI scan of the brain and additional imaging may be obtained as clinically indicated.

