6.1 Criteria for dose delays/dose modifications

In general, participants experiencing **Grade 1 and 2** drug related toxicities should not have the dose of BVD-523 modified. However, appropriate supportive care should be provided for the management of drug related toxicities. Grade 2 toxicities may require dose or schedule modifications (delaying or omitting individual doses) due to potentially greater clinical significance; however, this should occur after discussion with Principal Investigator.

Dosing of BVD-523 must be delayed if a participant experiences a **Grade 3 non-hematologic** toxicity. If the toxicity resolves (returned to baseline or decreased to Grade \leq 1) within 14 days, dosing of BVD-523 may be resumed with a 25% dose reduction.

Exceptions to this rule are as follows:

- Grade 3 fatigue persistent for \leq 7 days
- Grade 3 nausea, vomiting, or diarrhea persisting \leq 72 hours with maximum supportive care
- Grade 3 electrolyte events if they are resolved with replacement within 24 hours
- Lymphopenia regardless of grade
- The following grade 3 laboratory abnormalities will not be considered dose limiting if they return to baseline within 7 days: elevated bilirubin, AST, ALT, cholesterol, amylase, lipase, creatinine and hypertriglyceridemia

Dosing of BVD-523 must be delayed if a participant experiences the following **Grade 2 hematologic** toxicities:

- thrombocytopenia ($< 50,000/\mu\text{L}$)
- neutropenia ($< 1,000/\mu\text{L}$) lasting > 7 days

Dosing of BVD-523 must be delayed if a participant experiences the following **Grade 3 hematologic** toxicities:

- hemoglobin decrease (< 8.0 g/dL)
- grade 3 or 4 febrile neutropenia (defined as temperature $\geq 101^\circ\text{F}$ with a neutrophil count $\leq 1,000$ cells/ μL).

If the toxicity resolves (returned to baseline or decreased to Grade \leq 1) within 14 days, dosing of BVD-523 may be resumed with a 25% dose reduction

In the case of **Grade 4 hematologic or non-hematologic** (except alopecia) toxicity, **or persistent Grade 3** toxicity despite one dose level reduction, the dose level will be reduced by a

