total of 50 %. BVD-523 dose should not be reduced by more than 50 %. Participants unable to tolerate BVD-523 at a dose level of 50%, or whose drug related toxicity has not returned to baseline or Grade \leq 1 within 14 days, will be discontinued from study, unless clinical benefit has been demonstrated and a lower dose might, in the opinion of the PI, maintain clinical benefit.

Dose Level	BVD-523 Dose
-2	300mg, BID
-1	450mg, BID
0	600mg, BID

Nausea	Management/Next Dose for BVD-523
\leq Grade 1	No change in dose
Grade 2	Hold until \leq Grade 1. Resume at same dose level.
Grade 3	Hold* until $<$ Grade 2. Resume at one dose level lower, if indicated.**
Grade 4	Off protocol therapy
*Participants requiring a delay of $>$ 2 weeks should go off protocol therapy.	
**Participants requiring $>$ two dose reductions should go off protocol therapy.	
Recommended management: antiemetics.	

Diarrhea	Management/Next Dose for BVD-523
\leq Grade 1	No change in dose
Grade 2	Hold until \leq Grade 1. Resume at same dose level.
Grade 3	Hold* until $<$ Grade 2. Resume at one dose level lower, if indicated.**
Grade 4	Off protocol therapy
*Participants requiring a delay of $>$ 2 weeks should go off protocol therapy.	
**Participants requiring $>$ two dose reductions should go off protocol therapy.	
Recommended management: Loperamide antidiarrheal therapy	
Dosage schedule: 4 mg at first onset, followed by 2 mg with each loose motion until diarrhea-free for 12 hours (maximum dosage: 16 mg/24 hours)	
Adjunct anti-diarrheal therapy is permitted and should be recorded when used.	

Neutropenia	Management/Next Dose for BVD-523
\leq Grade 1	No change in dose
Grade 2	Hold until \leq Grade 1. Resume at same dose level.
Grade 3	Hold* until $<$ Grade 2. Resume at one dose level lower, if indicated.**
Grade 4	Off protocol therapy
*Participants requiring a delay of $>$ 2 weeks should go off protocol therapy.	
**Participants requiring $>$ two dose reductions should go off protocol therapy.	

Thrombocytopenia	Management/Next Dose for BVD-523
≤ Grade 1	No change in dose
Grade 2	Hold until ≤ Grade 1. Resume at same dose level.
Grade 3	Hold* until < Grade 2. Resume at one dose level lower, if indicated.**
Grade 4	Off protocol therapy
*Participants requiring a delay of >2 weeks should go off protocol therapy.	
**Participants requiring > two dose reductions should go off protocol therapy.	

Rash	Management/Next Dose for BVD-523

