Preclinical toxicity studies of BVD-523 provided evidence of exposure-related, reversible gastrointestinal toxicities, and these toxicities have also been observed at high frequency if the first 18 patients in the ongoing FIM Phase 1 study, in one case leading to an SAE of renal insufficiency secondary to dehydration. The severity and reversibility of these nonclinical and clinical toxicities, while not meriting a specific monitoring or treatment plan, warrant

active routine monitoring of patients for this toxicity.

QTc Prolongation

The balance of preclinical evidence suggests BVD-523 has low, but observable, potential to cause QT prolongation. Given potentially unique species sensitivity, as well as possibly unknown consequences following chronic dosing, patients dosed with BVD-523 are being monitored for potential QTc prolongation and any other related cardiotoxicities, including 12 hour Holter monitoring after the 1st and 3rd dose. No cardiac AEs have been reported in the first 18 patients treated with BVD-523 in doses up to 900 mg BID.

Tissue Mineralization

Tissue mineralization has been observed in rodent toxicology studies of BVD-523. The incidence and severity of mineralization was dose-dependent, and effects were observed in 1 or more tissues at toxic doses. In animals in which mineralization occurred after treatment with BVD-523, significantly increased serum phosphorus and modestly decreased serum calcium was seen; these effects were not observed in animals in which there was no mineralization.

Tissue mineralization has been reported in rodents with other compounds that target the MAPK pathway and published studies suggest that the MAPK pathway is a negative regulator of matrix mineralization both *in vitro* and *in vivo*.

Routine clinical laboratory tests, including blood chemistry analyses for calcium and inorganic phosphate, will be performed and any indication of abnormalities may result in further investigations. A clinical monitoring strategy similar to this was previously employed for related drugs that target the MAPK pathway.

Hematological Effects

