Hematological effects observed in a rat repeat dose study included lowered reticulocyte counts, mean corpuscular volume, platelet counts (in females only) and increased neutrophil, monocyte, basophil and large unstained cell counts. In dogs the clinical pathology findings were consistent with inflammation (increased white blood cell count, neutrophils, fibrinogen and globulin) and decreased albumin and hemorrhage (decreased red cell mass).

In order to monitor for potential hematologic toxicity in humans, routine clinical laboratory hematology tests, should be performed and any indication of abnormalities may result in further investigations.

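### No safety labs are scheduled at Cycle 1 Day 15, so the first scheduled on-treatment hematology and chemistry come at about Day 29; adding a panel to that visit is a cheap improvement

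*Combined protocol and SAP*

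**What the plan says.** - **Day 15 visit.** Section 5.2.3 lists two items: "Tumor biopsy between days 12-18 while on treatment" and "Collection of research blood sample for PK analysis prior to dosing". In the Section 10.1 calendar the Day 15 column is marked only for study drug, PK sample and biopsy. It is blank for hematology, serum chemistry, lipase/amylase and PT/aPTT. Footnote A has the patient take the morning dose in clinic that day.
- **Labs around it.** Section 5.2.1 says that most screening procedures, labs included, "are to be conducted within 21 days of Cycle 1 Day 1". Hematology and chemistry are repeated at Cycle 1 Day 1, which Section 10.1 places before dosing, and next at Cycle 2 Day 1. PT/aPTT is scheduled at screening and then at Cycle 2 Day 1.
- **Rules that use lab values.** Section 6.1 requires a delay for platelets below 50,000, neutrophils below 1,000 for more than 7 days, and hemoglobin below 8.0 g/dL. Its tables also hold the drug for Grade 2 neutropenia or thrombocytopenia until recovery ("Resume at same dose level"). Grade 3 non-hematologic toxicity requires a delay, but several Grade 3 chemistry abnormalities are excused if they return to baseline within 7 days.
- **Monitoring statements.** Section 7.2 says that "routine clinical laboratory hematology tests, should be performed and any indication of abnormalities may result in further investigations" and asks for "active routine monitoring of patients for this toxicity" in relation to gastrointestinal effects. Sections 7.2 and 8.1.1 rely on calcium and phosphorus in the routine chemistry to watch for tissue mineralization.

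**The concern.** The hold rules in Section 6.1 are mandatory and are driven by counts and chemistry, but for the first four weeks at 600 mg BID the schedule produces no value to feed them. An asymptomatic laboratory toxicity is what a scheduled test exists to find. Here the patient is already in clinic, about halfway through the cycle, having blood drawn before a dose. If the schedule is followed as written, that draw yields a PK tube and nothing that could trigger a hold. What is at stake is patient safety during Cycle 1 and the timeliness of the safety data, which serve the first secondary objective (Section 1.3).

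**Working it through.** The plan states no figure to reproduce. The check compares Section 5.2 with the Section 10.1 calendar and then counts days.

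**Inputs.** 28-day cycle and twice-daily dosing (Section 5.1); visit window of plus or minus 3 days (Section 10.1); first dose on Day 1; biopsy on Days 12 to 18 (Section 5.2.3 and Section 10.1) or 12 to 16 days after first treatment (Sections 9.0 and 13.6); screening labs up to 21 days before Day 1 (Section 5.2.1).

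**1. First scheduled on-treatment labs.** Cycle 2 Day 1 is Day 28 + 1 = 29, window 26 to 32. Time from first dose: 29 − 1 = 28 days (26 − 1 = 25 to 32 − 1 = 31). Doses: 28 × 2 = 56 (50 to 62). Even the earliest of these labs, Day 26, follows the latest biopsy under either stated window.

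**2. What a Day 15 panel gains.** For an abnormality present at the Day 15 draw that persists under dosing:
- nominal: 29 − 15 = 14 days sooner, or 14 × 2 = 28 doses;
- shortest: 26 − 18 = 8 days, or 16 doses;
- longest: 32 − 12 = 20 days, or 40 doses.

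**3. Average delay (assumption: onset uniform over Cycle 1, abnormality persists).** Day 29 only: 28/2 = 14 days. With Day 15 added: (14²/2 + 14²/2)/28 = 7 days (6.3 to 8.4 across the visit windows).

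**4. Delay or under-counting? (illustrative; uniform onset, no unscheduled labs).** The Day 29 draw alone would see 7/28 = 25% of abnormalities lasting 7 days, 14/28 = 50% of those lasting 14 days, and 100% of persistent ones. For persistent abnormalities the loss is delay, not a missed event.

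**5. Time-based clauses in 6.1.** The rule on neutropenia lasting more than 7 days and the 7-day return-to-baseline exception for chemistry both need a first abnormal value to start the clock. No scheduled test after first dosing supplies one in Cycle 1. A Day 15 panel can; the follow-up value would still be a clinically prompted draw.

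**6. Age of labs at biopsy.** Last scheduled platelet count (taken as Day 1): 12 − 1 = 11 to 18 − 1 = 17 days old. Last scheduled PT/aPTT: at most 21 + 17 = 38 days old. These are ages under the study schedule only. They do not show what the biopsy service will have in hand.

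**7. Event rate.** None can be derived. Section 7.2 gives no human cytopenia rate. It reports gastrointestinal toxicity "in one case leading to an SAE of renal insufficiency secondary to dehydration" among the first 18 phase I patients: 1/18 = 5.6%, exact 90% CI 0.3 to 23.8%. Its dose and timing are not stated, and Section 2.2 shows that the study dosed from 10 to 900 mg BID. It cannot serve as a rate for early laboratory-only toxicity at 600 mg.

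**The case against.** The strongest reply is that this is a permissible design choice that breaks no rule in the documents. The dose is the recommended phase II dose, with 48 patients already treated in its expansion cohort (Section 2.2). Eligibility requires adequate counts (Section 3.1.7). The animal evidence for cytopenia is thin: platelets fell in female rats only, neutrophils rose in rats and dogs, and the reduced red cell mass in dogs is attributed to hemorrhage (Section 7.2). Section 7.2 judges that gastrointestinal toxicity does not merit a dedicated monitoring plan; dehydration is usually symptomatic, and adverse events are collected from the first dose. No frequency is set for calcium and phosphorus, so testing once per cycle meets the wording. The 6.1 holds apply whenever a toxicity occurs, including one found on an unscheduled lab.

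Most of this stands, and it limits the size of the point. It does not remove it: an unscheduled lab needs a reason to be ordered, and asymptomatic changes give none.

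A reader might go further and infer that research biopsies, often of the liver, will be done without current platelets or coagulation results. The documents do not support that. Section 9.0 refers the lead institution to a Cross-Sectional Interventional Radiology (CSIR) biopsy protocol and other sites to institutional procedures. None of these is reproduced, and any may require pre-biopsy labs. Section 6.1 has no coagulation trigger, and Section 7.2 names no coagulation defect as a risk of BVD-523. Nor do the documents support reading the 6.1 holds as inoperable in Cycle 1; they lack a scheduled input, which is a narrower statement.

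**Conclusion.** The gap is real and Sections 5.2.3 and 10.1 agree on it: no hematology or chemistry is scheduled between the pre-dose Day 1 labs and Cycle 2 Day 1. Its consequence is a conditional delay, about two weeks, for a patient whose laboratory abnormality is present by Day 15, persists under dosing and is not picked up clinically. How many of the 13 to 25 patients that would be cannot be estimated from the documents. The averages in the working rest on an assumed uniform onset. The response endpoint is not directly affected, and for persistent abnormalities the safety tables would be late, not wrong. This is a cheap improvement to patient safety, not a defect that threatens the trial's conclusions.

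**What to change.** In Section 5.2.3 and the Day 15 column of Section 10.1, add hematology and serum chemistry with lipase and amylase. Draw them within the Day 12 to 18 window, with the PK sample where possible, and have them resulted before the biopsy. Add PT/aPTT only where the CSIR or institutional biopsy procedure does not already require it. Section 6.1, its thresholds and its time limits stay as they are.

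The cost is at most 25 routine panels (13 if the trial stops at stage 1), normally in the venipuncture already planned. A separate draw is needed only when the biopsy comes before the PK visit. Some panels will duplicate labs taken under local biopsy procedures. The document change is one line in 5.2.3 and a few entries in one calendar column.

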5.2.6 Cycle 3, Day 1 and beyond

Participants continuing BVD-523 dosing past Cycle 2 will repeat the schedule of events for Cycle 2, Day 1 with all required assessments with the following exceptions:

- Radiological imaging studies to evaluate tumor status will be repeated **during the last week (Days 22 to 28) of every second cycle** (e.g., Cycles 4, 6, 8, etc. only). Radiologic measurements should be performed every 8 weeks from C1D1 and this schedule should not be adjusted due to dose delay/modifications.

5.2.7 End of Treatment Visit

To be completed 20 to 30 days after the last dose of study drug.

- Physical examination
- Vitals (temperature, HR, BP and RR)
- Weight
- Performance status
- Record concomitant medications
- Laboratory Assessments

- Hematology
- Serum chemistry
- Serum lipase and amylase
- PT and aPTT
- Urinalysis
- Serum pregnancy test for WOCBP
- 12-lead ECG. If an ECG shows QTc prolongation (>470 milliseconds), the ECG must be repeated twice to obtain values in triplicate.
- Radiologic imaging studies: CT or MRI of chest, abdomen and pelvis followed by response evaluation to evaluate tumor status if the last scans were performed more than 4 weeks prior. MRI scan of the brain and additional imaging may be obtained as clinically indicated.
- Record AEs
- Eye Examination, will be performed by an ophthalmologist, or designated member of the clinical team, to check the participants vision and measure the pressure level in their eyes.

5.3 Agent Administration

5.3.1 BVD-523

BVD-523 is to be taken twice daily orally for 28 days, at 12 ±2 hour intervals at a dose of 600mg BID. This study drug dose will be supplied to participants in four 150 mg capsules. The study medication should be taken with 8 ounces of water (juice, coffee, tea or soda is not allowed) at the same time each day on an empty stomach (e.g. fasting or 30-60 minutes before food or 2 hours after food). Water is permitted during this period. At this time, there are no identified foods that participants should avoid while taking study drug. All capsules, if more than one is taken at each dosing time, should be taken within 10 minutes. Crushing, chewing, or dissolution in water is not advised. It is strongly preferred that participants take the medication as whole capsules. A participant that is observed to vomit an intact capsule after dosing in the clinic may receive a substitute dose of drug. However, participants should be instructed NOT to take a substitute capsule if vomiting occurs after self-dosing at home.

5.4 General Concomitant Medication and Supportive Care Guidelines

Because there is a potential for interaction of BVD-523 with other concomitantly administered drugs through the cytochrome P450 system, the case report form must capture the concurrent use of all other drugs, over-the-counter medications, or alternative therapies. Medications which are known to be strong inhibitors of CYP3A4, CYP2D6, and CYP1A2, or strong inducers of CYP3A4, are not permitted during the study (for list of non-permitted drugs see Appendix 1)

The Overall PI should be alerted if the participant is taking any agent known to affect or with the potential to affect selected CYP450 isoenzymes.

Medications taken within 14 days prior to Cycle 1, Day 1 and during the study will be collected on the participant's case report form. The following are the supportive care guidelines for the study:

- No other antineoplastic agents will be permitted during this study
- No concurrent radiation treatment will be permitted during this study, except for palliation or symptom relief on case by case basis following discussion with Principal Investigator
- No treatment with chronic immunosuppressants (e.g., cyclosporine following transplantation or systemic steroids for treatment of autoimmune disease) will be permitted during this study; however, use of inhalant steroids and steroids given for antiemetic purposes or supportive therapy for brain metastases are permitted
- The use of erythropoietin or other specific red blood cell growth factors and red blood cell transfusions will be permitted as clinically indicated during the study
- The use of bone marrow colony stimulating factors (such as granulocyte colony-stimulating factor or granulocyte-macrophage colony-stimulating factor) is permitted as clinically indicated
- Other concomitant medications may be given as clinically indicated
- Caution should be exercised when concomitant medications that are cleared predominantly by the CYP1A2, CYP2D6 and CYP3A4 pathways are administered.

The above information is precautionary only. Investigators are encouraged to discuss the use of individual medications with the Principal Investigator on a case-by-case basis.

